11.1.3 Outcome

The seriousness of an event is determined by its outcome (e.g., hospitalization, death, etc.). The action taken to treat an AE and the outcome of the action must be recorded. Outcomes may be categorized as shown below:

- FATAL: The termination of life as a result of an adverse event. Death Related to Adverse Event
- NOT RESOLVED: One of the possible results of an adverse event outcome that indicates that the event has not improved or recuperated.
- RESOLVED: One of the possible results of an adverse event outcome that indicates that the event has improved or recuperated.
- RESOLVED WITH SEQUELAE: One of the possible results of an adverse event outcome where the patient recuperated but retained pathological conditions resulting from the prior disease or injury.
- RESOLVING: One of the possible results of an adverse event outcome that indicates that the event is improving.
- UNKNOWN: Not known, not observed, not recorded, or refused.

11.1.4 AE Follow-Up

Any AEs that are ongoing after the Follow-up Visit should be followed for 30 days, with the exception of serious adverse events that are followed until resolution or stabilization. Information collected after the Follow-up Visit, however, will not be captured in the database, but will be maintained in the patient's study source records and made available upon request.

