9 STUDY PROCEDURES AND OBSERVATIONS

9.1 Study Procedures and Observations

Procedures	Visit 1**** (Screening) Day -28 to Day -7	Visit 1.1**** (Screening) Day -13 to Day -2	Visit 2 (Start of Placebo Lead-in) Day 1	Visit 2.1 (End of Placebo Lead-in) Day 13 (±2)	Screen* failure ONLY End of Study	Visit 3** (Baseline) Day 15 (+3)	Visit 4 (Week 2) Day 29 (±3)	Visit 5 (Week 4) Day 43 (±3)	Visit 6 (Week 6) Day 57 (±3)	Visit 7 (Follow-up) Day 71 (±3)	ET***	
											ET	Follow Up
Site Visit	X		X		X	X	X	X	X	X	X	X
Informed Consent (Study, PGx, HIPAA) ^a	X											
Demography	X											
Inclusion and Exclusion Criteria	X		X			X						
Evaluation of Medical and Psychiatric History	X		X									
Evaluation of Prior Medication History	X											
Serology Screen	X											
Urine Drug Screen	X					X						
Urine Pregnancy (all females)	X		X			X	X	X	X	X	X	X
Height	X											
Body Weight	X		X			X	X	X	X	X	X	X
Body Mass Index (BMI)	X											
Physical and Neurological Examination	X				X	X		X	X	X	X	X
Ophthalmological Examinations ^b			X					X	X	X	X	X
Columbia Suicide Severity Rating Scale (C-SSRS)	X				X	X	X	X	X	X	X	X
MINI	X											
HAM-D (SITE Rater)	X											
MGH ATRQ (Central Rater)		X										
HAM-D (Central Rater)		X		X								
SAFER Inventory (Central Rater)		X										
MADRS ^c						X	X	X	X	X		

A Multicenter, Randomized, Double-blind, Placebo-controlled Study of the Safety and Efficacy of TS-121 as an Adjunctive Treatment for Patients with Major Depressive Disorder with an Inadequate Response to Current Antidepressant Treatment

TS121-US201
Apr 23, 2018
Amendment 4

Procedures	Visit 1**** (Screening) Day -28 to Day -7	Visit 1.1**** (Screening) Day -13 to Day -2	Visit 2 (Start of Placebo Lead-in) Day 1	Visit 2.1 (End of Placebo Lead-in) Day 13 (±2)	Screen* failure ONLY End of Study	Visit 3** (Baseline) Day 15 (+3)	Visit 4 (Week 2) Day 29 (±3)	Visit 5 (Week 4) Day 43 (±3)	Visit 6 (Week 6) Day 57 (±3)	Visit 7 (Follow-up) Day 71 (±3)	ET***	
											ET	Follow Up
MADRS Central Rater Oversight						X ←————→				X		
CGI-S						X	X	X	X	X		
CGI-I							X	X	X	X		
HAM-A						X	X	X	X	X		
SDQ						X	X	X	X	X		
Vital Signs (seated)	X		X			X	X	X	X	X	X	X
12-Lead Electrocardiogram (ECG)	X					X	X	X	X	X	X	X
Clinical Laboratory Tests	X					X	X	X	X	X	X	X
Exploratory Safety Assessments			X			X	X	X	X	X	X	X
Hair Cortisol Level						X						
Plasma Copeptin Level						X			X			
Salivary Cortisol Level (at home) ^d			Dispense Kit			X						

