- If a death occurs and an autopsy is performed, a copy of the autopsy report should be obtained if possible when it becomes available. All efforts must be undertaken to obtain follow-up information promptly.

Any SAEs occurring from first administration of investigational product through 30 days after last administration must be reported. All SAEs will be reported, whether or not they are deemed to be related to study product. Timely reporting of SAEs will be followed in accordance with regulatory requirements as outlined in the Safety Plan.

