## **6.1.3.1 Adverse Events**

An adverse event (AE) is defined as any untoward medical occurrence in a patient administered an investigational product, and which does not necessarily have a causal relationship to investigational product. An AE can be any unfavorable or unintended sign (including an abnormal finding), symptom, or disease. AEs include any occurrence that is new in onset or aggravated in severity or frequency from the baseline condition, or abnormal results of diagnostic procedures (including clinically significant laboratory test abnormalities). AEs also include an intentional or accidental overdose, whether or not it is associated with symptoms. An overdose is defined as ingestion of the investigational product (accidental or intentional) more than 3 capsules in the same calendar day.

AEs will be recorded after the first administration of the investigational product in the placebo lead-in period through follow-up. AEs with onset date and time (if available) after the first administration of randomized treatment will be considered treatment emergent AE (TEAE).

Any AEs with incomplete start and end dates/times will be treated as follows:

- Adverse events with unknown start and/or end times (but where the date is known) will be imputed as post-dose for events on first treatment day of placebo lead-in or randomized treatment or with a time of 00:00 for other days. The missing time will be shown blank in the listings.
- Adverse events with incomplete start day and known month will be imputed as the later of: day of first placebo lead-in dose or first randomized dose started in that month or first of the month. Missing day will be printed -- in the listings.
- Adverse events with incomplete start dates missing month and day will be considered as the later of: day of first placebo lead-in dose or first randomized dose started in that year or January 1. Missing month and day will be printed ----- in the listings.
- Adverse events with completely unknown start dates will be considered as treatment emergent for the tabulations and the missing dates will be shown as ----- in the listings.

Details of AE classification for severity (mild, moderate or severe), action taken and relationship to test drug (not related, possibly related, probably related and definitely related) are provided in Appendix C. All AEs will be coded using MedDRA Version 19.1.

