# Statistical Analysis Plan

Taisho Pharmaceutical R&D Inc.  
Protocol TS121-US201

Statistical Analysis Plan (SAP)

Final 2.0  
18 Dec 2018  
CONFIDENTIAL

median and maximum) will be calculated for each quantitative variable (unless otherwise stated).

All statistical programming will use SDTM data and will be based on SDTM mapping rules for scheduled, unscheduled and repeat visits. No assessment or exclusions other than the mapping specifications will be performed for visits out of the planned visit window.

Listings will include repeat and unscheduled measurements.

The following rules will apply to repeat and unscheduled measurements in summary tables:

- No more than one assessment per patient per time point will be used in the summary of each scheduled safety or efficacy endpoint.
- If the repeated measurement occurs prior to the first dose of study drug for the treatment period, then the last obtained value of any repeated measurement will be used as baseline in the summary tables.
- If the repeated measurement occurs after the first dose of study drug for the treatment period, then the first obtained value of any repeated measurements will be used in the summary tables.

Unless specified otherwise, the baseline used for any change from baseline measurements will be the last measurement prior to the first dose of study drug for the treatment period.

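### SAEs are reportable to 30 days after last dose and followed to resolution, but information collected after the Follow-up Visit, about 14 days after last dose, is kept out of the database behind the SAE outputs.

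*Protocol*

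**What the plan says.** - **Reporting window.** Protocol 11.2.2: "Any SAEs occurring from first administration of investigational product through 30 days after last administration must be reported". Reports are due within 24 hours of awareness, whether or not the event is judged related.
- **Follow-up of events.** Protocol 11.1.4: "Any AEs that are ongoing after the Follow-up Visit should be followed for 30 days". SAEs are the exception and are followed until they resolve or stabilize. Protocol 11.2.3 repeats this for SAEs ongoing at the end of the study or at discontinuation.
- **Database cut-off.** The next sentence of 11.1.4 reads: "Information collected after the Follow-up Visit, however, will not be captured in the database". That information stays in source records and can be requested. The sentence makes no exception for SAEs.
- **Timing of the visit.** Protocol 9.1 puts Visit 6 at Day 57 and Visit 7 at Day 71, each ±3 days. Patients who stop early have a follow-up visit about 14 days after last dose (Protocol 6.5). The schedule ends AE inquiry at Visit 7 or at the early-termination follow-up.
- **SAP.** Section 6.1.3.1: "AEs will be recorded after the first administration of the investigational product in the placebo lead-in period through follow-up". Section 6.3.1: "All statistical programming will use SDTM data". Section 6.3.16.1 puts end date and outcome in the AE listings, counts patients with any SAE in the overview (Table 14.3.1.1) and summarizes SAEs in Table 14.3.2.1.

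**The concern.** The protocol sets one end point for SAE reporting and an earlier one for what enters the database, and the SAP builds its outputs on the database. Neither document says how an SAE report received between the two is to reach the tables and listings.

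Safety and tolerability is the first-listed primary objective. Earlier exposure was 78 healthy subjects, with 50 mg given for 10 days at the highest dose level (Protocol 4.4.2); this trial doses patients for six weeks. Ventricular arrhythmias judged possibly related to the drug were seen in Phase 1 (Protocol 4.4.3). The study report could therefore show an SAE as unresolved when the safety reports hold a worse outcome, or could show fewer SAEs than were reported within the protocol's own window.

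**Working it through.** **Which information is cut off.** There are two readings of the sentence in 11.1.4.

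1. *Narrow: only later information on events already ongoing at the visit.* The preceding sentence names SAEs explicitly, so they are in scope. Protocol 11.2.1 treats death as an outcome, with its cause as the SAE, and Protocol 11.1.3 lists fatal and resolved with sequelae among the outcome categories. A death after the visit from an SAE already recorded is therefore an outcome update, which is what the sentence keeps out. The SAE count is unaffected; the outcome and end date in Listing 16.2.7.2 would be out of date.
2. *Wide: all information collected after the visit.* The sentence is unqualified, and the schedule ends AE inquiry at the same visit. SAEs starting after the visit would then also be absent from Table 14.3.2.1, Listing 16.2.7.2 and Table 14.3.1.1.

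**How much time is involved.** Inputs:

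- Visit 6 on Day 57 ±3 and Visit 7 on Day 71 ±3 (Protocol 9.1).
- Last expected dosing day = Visit 6 day (compliance formula, SAP 6.1.4), so nominally Day 57.
- First lead-in dose on Day 2 and first randomized dose on Day 16 (Protocol 9.1, footnote e).
- SAE reporting to last dose + 30 days (Protocol 11.2.2).

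The plan's own figure first: 71 − 57 = 14 days, which agrees with the two weeks stated in the synopsis.

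Uncaptured days = (last dose + 30) − Visit 7 day. Nominally (57 + 30) − 71 = 87 − 71 = 16 days.

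Uncaptured days with both visits moved within their windows:

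| Last dose = Visit 6 | Visit 7 on Day 68 | Visit 7 on Day 71 | Visit 7 on Day 74 |
|---|---|---|---|
| Day 54 | 16 | 13 | 10 |
| Day 57 | 19 | 16 | 13 |
| Day 60 | 22 | 19 | 16 |

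The same gap against three denominators:

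| Denominator | Nominal | Over the visit windows |
|---|---|---|
| 30 post-dose days | 16/30 = 53% | 10/30 = 33% to 22/30 = 73% |
| Full window, Day 2 to Day 87 (86 days) | 16/86 = 19% | 10/83 = 12% to 22/89 = 25% |
| From first randomized dose, Day 16 to Day 87 (72 days) | 16/72 = 22% | 10/69 = 14% to 22/75 = 29% |

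The ranges hold Days 2 and 16 fixed. If the last dose is taken the day before Visit 6 (Day 56), the nominal gap is 86 − 71 = 15 days, or 15/30 = 50%. For early discontinuations the nominal gap is 30 − 14 = 16 days.

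**The case against.** The strongest reply is that 11.1.4 concerns follow-up of existing AEs. On that view the sentence deals only with continued follow-up and says nothing about SAEs starting after the visit, which belong to 11.2.2. The SAP gives this some support. Section 6.3.1 defines the follow-up period as any visit or study day after Week 6/EOT, so recording through follow-up in 6.1.3.1 need not stop at Visit 7, and the treatment-emergent definition in 6.3.16.1 has no upper time limit. This stands as far as it goes: loss of new-onset SAEs is an inference from the unqualified wording and the end of AE inquiry, not an explicit rule. It does not remove the loss of later outcomes, which follows on either reading.

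Other points stand as limits:

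- SAE handling is referred to a Safety Plan and database procedures to a Data Management Plan, neither of which is available here. A reconciliation step may exist in one of them. It would still have to be squared with the exclusion written in 11.1.4.
- Every SAE in the window still goes out within 24 hours and is followed. The point concerns data capture for the study report, not safety oversight.
- The missed days are all off treatment, and Phase 1 reported no deaths or SAEs. A share of days is not a share of events.

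A reader might infer that the SAE tables miss about half of the mandated reporting window. The documents do not support that: the window in 11.2.2 opens at first administration, so the nominal gap is 19% of it, and 53% applies only to the 30 post-dose days. Nor do they show that late SAEs can never reach the tables; the written rules exclude them on the wide reading, but an unseen procedure could bring them in.

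**Conclusion.** The inconsistency is real and should be resolved. As written, outcomes of SAEs that change after the Follow-up Visit, including to fatal, will not reach the database or the outputs built on it. On the wider and plausible reading, SAEs starting after the visit will be missing too. The uncaptured time is nominally 16 of 30 post-dose days (53%; 10 to 22 days, 33% to 73%, over the visit windows), or 19% of the full Day 2 to Day 87 window.

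These figures assume that the last dose falls on the Visit 6 day and that visits fall within their windows. The number of SAEs affected cannot be estimated, because the documents give no SAE rate. It would go too far to conclude that the reported SAE count will be wrong or will differ from the safety reports. What can be said is that nothing in the protocol or SAP makes the two agree.

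**What to change.** - **Protocol 11.1.4:** reconcile it with 11.2.2 by limiting the database exclusion to non-serious AEs. State that SAE onset, outcome and relationship are entered in the clinical database through 30 days after last dose.
- **SAP 6.1.3.1 and 6.3.16.1:** state that the SAE tables and listings cover that window after reconciliation with the safety reports. An SAE still unresolved at 30 days can be shown as ongoing at the cut-off.

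The cost is one changed sentence in each document, the amendment and IRB submission that Protocol 14.1 requires, and a reconciliation step. Database lock would fall nominally about 16 days after the last follow-up visit, and up to about 22 days at the extremes of the visit windows. Nothing changes in dosing, visits or patient care.

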11.2 Serious Adverse Event Reporting

11.2.1 Definition of Serious Adverse Event

A serious adverse event (SAE) is an untoward medical occurrence that at any dose:

- results in death (Note: Death is an outcome and not an event and the cause of death should be listed as the SAE);
- is life-threatening (i.e., the patient was at immediate risk of death from the AE);
- requires inpatient hospitalization or prolongation of existing hospitalization;
- results in persistent or significant disability/ incapacity; or
- is a congenital anomaly or birth defect (in the child of a patient who was exposed to the investigational product)

Any other important medical event that may result in death, be life-threatening, or require hospitalization, may be considered a SAE when, based upon appropriate medical judgment, the event may jeopardize the patient and may require medical or surgical intervention to prevent one of the outcomes listed above.

11.2.2 Serious Adverse Event Reporting Procedure

If in the opinion of the investigator, the event meets the criteria of an SAE, the following procedures will be followed:

On discovery, all SAEs should immediately (within 24 hours of awareness of the event) be reported to [REDACTED] by:

- Completing the SAE report form and faxing the documents to [REDACTED], using the [REDACTED] SAE fax number below:
 - 24/7 Fax: [REDACTED]
- Or, by completing the SAE report form and submitting it to [REDACTED] via email utilizing the address below:
 - SAE Reporting e-mail: [REDACTED]
- In the event that the site is unable to complete the SAE form to report the event within 24 hours of awareness of the event, the investigator may report the SAE over the telephone and then provide the completed SAE form via (fax/email). If questions arise regarding the reporting procedures or the specifics of the reporting of an event, the site may call utilizing the following number:

[REDACTED]

- The following documents will be forwarded to [REDACTED] within 24 hours of reporting the event:
 1. SAE Report
 2. Con Med CRF page
 3. Medical History page
 4. Any other applicable information
- The sponsor must be notified within 24 hours of awareness of the event as specified in the Safety Plan.
- The initial report of an SAE may be submitted by email. The investigator must provide the minimal information: i.e. the protocol number, subject number, date of SAE, SAE term,

short description of the event, causality (if determined) and the reason why the event is categorized as serious.

- The investigator will also notify the Institutional Review Board (IRB) of the event within the time frame specified in the IRB's Standard Operating Procedures after becoming aware of the SAE. An initial report followed promptly by a complete report will be forwarded to the IRB, or in accordance with the IRB policy.
- The patient will be observed and monitored carefully until (1) the condition stabilizes and/or resolves; (2) its cause is identified; or (3) it is otherwise determined by the Medical Monitor and investigator. Follow-up information relating to the SAE must be submitted to [REDACTED] by email as soon as additional information related to the event is available.
- If a patient is hospitalized due to the SAE, the hospital discharge summary should be obtained if possible when it becomes available.
- If a death occurs and an autopsy is performed, a copy of the autopsy report should be obtained if possible when it becomes available. All efforts must be undertaken to obtain follow-up information promptly.

Any SAEs occurring from first administration of investigational product through 30 days after last administration must be reported. All SAEs will be reported, whether or not they are deemed to be related to study product. Timely reporting of SAEs will be followed in accordance with regulatory requirements as outlined in the Safety Plan.

11.2.3 SAE Follow-Up

If an SAE is reported while the event is still ongoing, the investigator must submit follow-up reports to [REDACTED] regarding the patient's subsequent course. All SAEs, including those that are ongoing at the end of the study or upon discontinuation must be followed until resolution or stabilization.

11.3 Events of Clinical Significance

Suicidal ideation and behavior, and lens opacity, as defined in the following sections, are considered as Event of Clinical Significance (EOCS). An EOCS should be recorded as an AE. All EOCS, regardless of whether the event meets criteria for SAE, should be reported to [REDACTED] within 24 hours of becoming aware of the event.

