4.4.2 Summary of Clinical Findings

Three Phase 1 studies, a single ascending dose (SAD) study (TS121-US101), a multiple ascending dose (MAD) study (TS121-US102), and a positron emission tomography (PET) receptor occupancy study (TS121-US103) have been conducted. Overall, 78 healthy male and female adult subjects were administered TS-121 to date. A top dose of 50 mg for 10 days was deemed safe and well tolerated. There were no deaths or serious adverse events reported in any of the studies.

Treatment emergent ventricular arrhythmias have been reported following single and multiple dose administrations of TS-121.

No safety trends were observed in clinical laboratory, vital signs, or physical examinations. In consideration of the nonclinical findings at the time of the MAD study, comprehensive eye examinations were performed; no abnormalities in the eyes relating to lens opacity were reported, including at the highest dose level of 50 mg for 10 days.

Additional details are described in Sections 8 and 9 of the Investigator's Brochure.

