4.4.3 Known and Potential Risks to Human Subjects

Though the relevance to human subjects is not yet fully understood, nonclinical findings suggested that potential risks include cataract, hepatotoxicity, effects on the gastrointestinal system and effects on the renal system. To date, no apparent trends related to these potential risks were noted in the clinical studies.

Treatment emergent ventricular arrhythmias have been reported following single and multiple dose administrations of TS-121. During the SAD study (TS121-US101), two subjects exposed to 2.5 mg of TS-121 had defined intervals of ventricular arrhythmias while on telemetry. Plasma levels were approximately 50% of C_{max} values (40 to 70 ng/mL). The events were without symptoms, resolved without intervention, and produced no residual effects. The events were considered mild in intensity and possibly related to the study drug. One subject was discontinued from the trial, and one subject completed the trial.

In the MAD study (TS121-US102), one subject showed a single episode of 4 consecutive premature ventricular contractions without symptoms while on telemetry approximately 15 hours

after receiving 50 mg dose of TS-121 on Day 9. The investigator assessed the episode as a clinically significant event and described the event as mild and possibly related to TS-121. The subject completed the trial with no additional events.

In a PET receptor occupancy study (TS121-US103), no abnormal ECG results were reported following single TS-121 doses of up to 50 mg. See Sections 8 and 9 of the Investigator's Brochure for additional information.

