## Event of Clinical Significance

AEs that are suicidal ideation and behavior or lens opacity, as defined in the CSP Section 11.3, will be recorded as events of clinical significance (EOCS).

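### The Event of Clinical Significance scheme omits ventricular arrhythmia, so a non-serious case has no 24-hour rule in the protocol text and no grouped count by arm

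*Protocol*

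**What the plan says.** Protocol 11.3 names two kinds of event: "Suicidal ideation and behavior, and lens opacity, as defined in the following sections, are considered as Event of Clinical Significance (EOCS". The consequence is prompt reporting: "All EOCS, regardless of whether the event meets criteria for SAE, should be reported to" a recipient whose name is blacked out, within 24 hours of awareness. Section 6.4 also lets the sponsor break the blind for these events. SAP 6.1.3.1 carries over the same scope: "AEs that are suicidal ideation and behavior or lens opacity, as defined in the CSP Section 11.3".

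On the heart, Protocol 4.4.3 states: "Treatment emergent ventricular arrhythmias have been reported following single and multiple dose administrations of TS-121". In the single-dose study, "two subjects exposed to 2.5 mg of TS-121 had defined intervals of ventricular arrhythmias while on telemetry". In the multiple-dose study, after 50 mg, "one subject showed a single episode of 4 consecutive premature ventricular contractions without symptoms while on telemetry". All three cases were called mild and possibly related. The investigator judged the multiple-dose case clinically significant, and one of the two single-dose subjects was discontinued. The PET study reported no abnormal ECG after single doses of up to 50 mg.

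On the lens, Section 4.4.3 traces the cataract risk to nonclinical findings. For the multiple-dose study, Section 4.4.2 reports that "no abnormalities in the eyes relating to lens opacity were reported".

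**The concern.** Of the findings in the protocol's own risk section, ventricular arrhythmia is the one described as treatment-emergent in people, with individual cases. The expedited list covers a nonclinical lens signal and suicidality but not this finding, and neither document gives a reason.

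Safety is a primary objective. Dosing goes from at most 10 days at 50 mg in healthy subjects to six weeks in patients who also take an antidepressant. The Phase 1 cases were asymptomatic and mild, and Section 4.4.2 reports no serious adverse event in those studies. A repeat would most likely be recorded as an ordinary adverse event. Two things are at stake: how soon the sponsor hears of such a case, and whether a handful of cases under different terms would be seen together when the arms are compared.

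**Working it through.** The plan gives no figure to reproduce, since the sample size rests on practical grounds (Protocol 10.1). The check follows a non-serious ventricular arrhythmia through the rules, with a Class I lens event beside it.

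**Step 1. Coverage**

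| Provision | Class I lens event | Non-serious ventricular arrhythmia |
|---|---|---|
| 24-hour report whatever the seriousness (Protocol 11.3, 11.3.2) | Yes | No |
| 24-hour report through the SAE rules (11.2.1, 11.2.2) | If it qualifies as serious | Only if medical judgment makes it an important medical event |
| Named supporting documents (11.3.3) | Examination results and photographs | None |
| Unblinding (6.4) | EOCS route and emergency route | Emergency route only |
| Becomes an AE | Always (11.3.2) | Always if the ECG is read as abnormal and clinically significant; not required by SAP 6.1.3.4 if read as Abnormal NCS |
| General by-arm AE tables 14.3.1.2 and 14.3.1.3 (SAP 6.3.16.1) | Yes | Yes, once recorded as a treatment-emergent AE |
| Table 14.3.2.2 and Listing 16.2.7.4 | Yes | No |
| ECG-interpretation Table 14.3.6.2.4 (SAP 6.3.16.4) | Not applicable | Yes, by arm and visit, type not shown |
| Output that brings the cases together | Tables 14.3.2.2 and 14.3.6.4.1 | None |

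The arrhythmia is therefore tabulated, but not as a group. Tables 14.3.1.2 and 14.3.1.3 count by preferred term, so related terms occupy separate rows. Table 14.3.6.2.4 counts readings by the investigator's category, so a ventricular finding cannot be told from any other abnormality.

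**Step 2. The Phase 1 rate**

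- Cases: 2 (single-dose study) + 1 (multiple-dose study) = 3, taken as distinct subjects.
- Denominator, from Protocol 4.4.2: "Overall, 78 healthy male and female adult subjects were administered TS-121 to date".
- Rate: 3/78 = 0.0385, or 3.8%.
- Exact (Clopper-Pearson) 95% limits: the 0.025 quantile of Beta(3, 76) = 0.0080 and the 0.975 quantile of Beta(4, 75) = 0.1083, so 0.8% to 10.8%.

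**Step 3. What that rate can and cannot carry**

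Two arms of 60 give 120 patients on TS-121. If the Phase 1 rate applied, which is an assumption, the expected number of affected patients would be 120 × 0.0385 = 4.6, with a range of 120 × 0.0080 = 1.0 to 120 × 0.1083 = 13.0. These are occurrences at a telemetry rate. In this trial a standard 12-lead ECG is taken at visits (Protocol 9.1, 9.2.7.7). During double-blind dosing the scheduled ones are at Weeks 2, 4 and 6, so three per completer between Day 16 and Day 57, or 57 − 16 + 1 = 42 days. The documents give no basis for converting occurrences into detections.

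**The case against.** The strongest reply has four parts.

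- **The events are tabulated.** A reader might infer that a non-serious arrhythmia is not counted by arm at all. The documents do not support that. SAP 6.3.16.1 counts treatment-emergent AEs by arm with no seriousness filter, and Table 14.3.1.2 is marked top-line, as is the EOCS table. SAP 6.3.16.4 counts ECG interpretations by arm and visit, and the listings carry verbatim terms and interpretations. This part stands in full. What remains is the missing grouped count.
- **Other routes exist.** A reader might also infer that such an event can be neither expedited nor unblinded. That goes too far. The important-medical-event clause can make it an SAE with a 24-hour report, and Section 6.4 allows unblinding where knowing the treatment would guide emergency care. The SAE route is discretionary, however, and the Phase 1 pattern of mild, asymptomatic episodes is unlikely to trigger either.
- **Unseen material may settle it.** The protocol refers to a Safety Plan for reporting and unblinding details, and to the Investigator's Brochure for Phase 1 detail. Part of the background is redacted. Any of these could hold an arrhythmia rule or the reason for singling out the lens. This stands as a limit: the point concerns the protocol and SAP text only.
- **The signal is weak.** The 3/78 pools three studies without a placebo rate, and two of the three cases were at 2.5 mg, a dose not used here. The documents do not say whether all 78 subjects were on telemetry. This stands, and it rules out reading 4.6 as a forecast for this trial.

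Nor is there a strict contradiction, because no passage requires every Phase 1 finding to be an EOCS. It is a mismatch between the risk section and the reporting list, left unexplained.

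**Conclusion.** The concern holds in a limited form. By the text of both documents, a non-serious ventricular arrhythmia has no 24-hour rule unless it is judged an important medical event, no place in the EOCS table or listing, and no pooled count by arm. It does appear by arm in the general AE tables, once recorded as an AE, and in the ECG-interpretation table.

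The size is uncertain. The Phase 1 rate of 3.8% (0.8% to 10.8%) shows why the finding deserves attention. It does not establish causality or say how many cases visit ECGs will show. The conclusion assumes that the Safety Plan does not already cover arrhythmia and that the three Phase 1 cases were different people. It is a worthwhile, low-cost improvement to safety reporting, and it does not affect the validity of the efficacy analysis.

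**What to change.** **Protocol.** Reconcile Sections 4.4.3 and 11.3. Add ventricular arrhythmia to the events reported within 24 hours, with the ECG tracing among the documents listed in Section 11.3.3. The sponsor's medical and safety team should set the definition, because the documents supply no threshold. State whether the EOCS unblinding route in Section 6.4 applies to it. If the Safety Plan already has such a rule, refer to it. If the omission is deliberate, give the reason.

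**SAP.** Bring the EOCS definition in 6.1.3.1 into line. Before unblinding, prespecify a grouped set of ventricular-arrhythmia preferred terms together with the relevant ECG interpretation findings. Count each patient once, by arm, in one added row of Table 14.3.2.2. The SAP describes the interpretation only as a three-level category, so confirm that the database holds the finding itself. If it does not, the row rests on AE terms alone and should say so. The row can be added even if the protocol list stays as it is.

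**Cost.** A few more expedited reports, one more table row, and no new procedure. The real trade-off is unblinding: if the Section 6.4 route is extended, asymptomatic ECG findings could lead to more broken codes. That is why its application should be stated rather than left to follow from the EOCS label.
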